7.2 Rationale for Study Design and Treatment Regimens

The objectives of this study are to obtain efficacy, tolerability, and safety data for the selected two doses ([REDACTED] and [REDACTED]/day) of MT-7117 and placebo when administered to adults and

MT-7117-G01 Protocol

Final Version 4.1, 9 August 2021

Confidential

Page 34 of 243

adolescents with EPP or XLP over a 26-week treatment period. A standard randomized, placebo controlled, double-blind treatment allocation is considered appropriate in order to obtain unbiased results in this study. Safety, PK, PD, and efficacy effects will be evaluated based upon the comparable data from the Phase 1 (MT-7117-E01, MT-7117-E02, MT-7117-E03, and MT-7117-A02) and Phase 2 (MT-7117-A01) studies.

Abnormal changes in biochemical markers related to the hepatic function were observed in rats and monkeys. In MT-7117-E01 human study, in subjects receiving 14 days of study drug, treatment-emergent transaminase elevations were reported in 6/36 (17%) subjects receiving MT-7117 and 2/12 (17%) subject receiving placebo. Of the six subjects receiving MT-7117 for 14 days reporting treatment-emergent transaminase elevations, 4 had elevated baseline transaminase values. Therefore, frequent assessments of liver function markers are performed in this study. However, in Study MT-7117-A01 hepatic AEs and increase in hepatic laboratory parameters were comparable between MT-7117 and placebo subjects.

The 26-week treatment period is considered a sufficient duration for evaluation of the efficacy and tolerability of MT-7117 for this study. Subjects will be offered to enroll in the 26-week double-blinded extension period starting immediately at the last visit in the double-blind treatment period. Subjects will attend a follow-up visit 6 weeks after the end of treatment (or early termination visit) which is considered a sufficient duration to evaluate pigmentation recovery and safety of subjects. For the primary and secondary endpoints, the effect of MT-7117 on the time to first prodrome associated with sunlight exposure will be measured using an electronic sunlight exposure diary. Melanin density assessments are safe and routinely used in clinical studies of skin disorders. Melanin density assessments were used in the MT-7117-A01 study and will be used in this study to assess the effect of MT-7117 on pigmentation. The effect of MT-7117 on QOL will be assessed using validated questionnaires.

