2.3.4 Exploratory Efficacy Endpoint for Double Blind Extention (DBE) Data Analysis

- Change from baseline in average daily sunlight exposure time (minutes) to first prodromal symptom (burning, tingling, itching, or stinging) associated with sunlight exposure between 1 hour post sunrise and 1 hour pre-sunset at each timepoint.
- Patient Global Impression of Change (PGIC) at each visit.
- Total number of sunlight-induced pain events defined as prodromal symptoms (burning, tingling, itching, or stinging) with pain rating of 1-10 on the Likert scale during each 26-week double-blind extention treatment.
- Change from baseline for all total score and total score in each domain the PROMIS-57 at each visit.
- The percentage of subjects who are responders based on average daily sunlight exposure time to first prodromal symptom associated with sunlight exposure between 1 hour post sunrise and 1 hour pre-sunset defined by within-subject meaningful change of 66 minutes increase from baseline at each time point.
- Change from baseline for in-clinic sunlight exposure time (minutes) to the first prodromal symptoms or end of test, whichever comes first.
- Total time (hours) during the 26-week double-blind extention period in duration of sunlight exposure between 1 hour post sunrise and 1 hour pre-sunset without prodromal symptoms.
- Total time (hours) during the 26-week double-blind extention period in duration of sunlight exposure between 1 hour post sunrise and 1 hour pre-sunset without prodromal symptom with the severity of greater than 0 on an 11-point Likert scale and without phototoxic reactions (pain-free time hours).
- Change from baseline in the average daily mean intensity on an 11-point Likert scale of the subject's prodromal symptoms over time during the 26-week double-blind extention period.

- Change from baseline in average daily duration (minutes) of prodromal symptoms during the 26-week double-blind extention period
- Total number of sunlight-induced pain events defined as phototoxic events during the 26-week double-blind extention period
- Total number of sunlight-induced non-prodrome, phototoxic reactions during the 26-week double-blind extention period.
- Change from baseline in the average daily mean intensity of the subject's phototoxic reactions (associated with sun exposure) during the 26-week double-blind extention period on an 11-point Likert scale.

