Subjects will be offered participation in a 6-month extension where all participants are on active drug but are double-blinded to dose starting immediately after the end of the 26-week doubleblind treatment period. If study subjects elect to participate in the 26-week DBE after end of Visit 7 (EOT/Rand), subjects will remain blinded and subjects will be re-randomized. Subjects that received MT-7117 during the blinded period will continue the DBE in the same treatment arm and remain blinded. Subjects that received placebo will be randomized to receive MT-7117 [REDACTED] or [REDACTED] in 1:1 ratio for the 26 weeks DBE period. [REDACTED]

[REDACTED] the [REDACTED] dose will be administered without re-randomization.

During the DBE, subjects will attend an in-clinic visit at Week 39 (Visit 10) where measurements will be performed. In addition, subjects may undergo mobile laboratory or in-clinic visits for sample collection at Weeks 28 and 32 (Visits 8 and 9, respectively) to measure liver function markers (AST, ALT, GGT, ALP, direct and total bilirubin).

Subjects will attend the end of treatment visit at Week 52 or early termination visit (Visit 11). Following the last treatment visit, subjects will attend a follow-up visit at Week 58 (Week 32 if DBE is not elected) or 6 weeks after early termination visit.

Subjects who are permanently withdrawn from study drug early should be encouraged to continue in the study and complete all other study assessments without receiving study drug. If a patient decides to completely withdraw consent/assent from the study, every attempt should be made to have the patient complete an early termination visit (Visit 7 or Visit 11).

[figure not shown]

Figure 1 Study Design Schematic

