7.1 Treatment Group Definitions and The Corresponding Analyzed Period Data

Two treatment group definitions for DBT data analysis and for DBE data analysis will be used as follows:

For DBT period data analysis

All DBT period data in all Subject type and Follow up period data in Subject type A, B, C and D in Section 4.1 will be analyzed with the below definition.

Treatment Group	Definition
MT-7117 [REDACTED]	Allocated to MT-7117 [REDACTED] group in DBT period
MT-7117 [REDACTED]	Allocated to MT-7117 [REDACTED] group in DBT period

Treatment Group	Definition
Placebo	Allocated to Placebo group in DBT period

For DBE period data analysis

All DBE period data and all Follow up period data in Subject Type A and B in Section 4.1 will be analyzed with the below definition.

Treatment Group	Definition
MT-7117 [REDACTED]	Allocated to MT-7117 [REDACTED] group in DBT period and Enrolled in DBE period.
MT-7117 [REDACTED]	Allocated to MT-7117 [REDACTED] group in DBT period and Enrolled in DBE period.
MT-7117 [REDACTED] (switched from Placebo)	Allocated to Placebo group in DBT period and switched to MT-7117 [REDACTED] group in DBE period.
MT-7117 [REDACTED] (switched from Placebo)	Allocated to Placebo group in DBT period and switched to MT-7117 [REDACTED] group in DBE period.

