7.3 Analysis Visit Definitions

(1) eDiary data excluding in-clinic sunlight exposure test

The subjects will, in their diaries, record the sunlight exposure periods (start/end time), prodromal symptom periods, and pain periods. The subjects' sunlight exposure start and end times will be compared with their state capital cities sunrise and sunset times.

The analysis windows are defined in the table below. The nominal day for each week relative to the first dose day will be used. Day 1 is the first dose day.

Table 2 Analysis Visit Window for diary data

Analysis Visit	Nominal day	Analysis Visit Window for DBT analysis
Baseline*	Day 1	Day -14 to -1
Week 2	Day 15	Day 1 to 14
Week 4	Day 29	Day 15 to 28
Week 6	Day 43	Day 29 to 42
Week 8	Day 57	Day 43 to 56
Week 10	Day 71	Day 57 to 70
Week 12	Day 85	Day 71 to 84
Week 14	Day 99	Day 85 to 98
Week 16	Day 113	Day 99 to 112
Week 18	Day 127	Day 113 to 126
Week 20	Day 141	Day 127 to 140
Week 22	Day 155	Day 141 to 154
Week 24	Day 169	Day 155 to 168
Week 26 (DBT EOT)	Day 183	Day 169 to 182
Week 26 (DBE Baseline)	Day 183	Day 169 to 182
Week 28	Day 197	Day 183 to 196
Week 32	Day 225	Day 211 to 224
Week 39	Day 274	Day 260 to 273
Week 52 (DBE EOT)	Day 365	Day 351 to 364
EOT for DBT	Day 182 or discontinued during DBT	14 days before EOT for DBT
EOT for DBE	Day 365 or discontinued during DBE	14 days before EOT for DBE
Follow-up until Week 32 (DBT EOS)	6 weeks after EOT for DBT	the latest 1 to 14 days before Follow-up date not overlapping with treatment duration in DBT period
Follow-up until Week 58 (DBE EOS)	6 weeks after EOT for DBE	the latest 1 to 14 days before Follow-up date not overlapping with treatment duration in DBE period

During 26 weeks (DBT)	1 to 182	Day 1 to EOT for DBT period
During 26 weeks (DBE)	183 to 364	DBE Baseline to EOT for DBE period

* If subjects have at least 1 day between Day -1 and Day -14, the baseline value will be calculated from the data between Day -1 and Day -14. If subjects have no data of sunlight exposure between Day -1 and Day -14, then the Analysis Visit window will be expanded to Day -28 and the baseline value will be calculated from the data between Day -1 and Day -28.

(2) Non-diary data including in-clinic sunlight exposure test

Table 3 Analysis Visit Window for non-diary efficacy data

Analysis Visit	Nominal day	Analysis Visit Window
Baseline	First dose day	NA
Week 4	Day 29	Day 16 to 64
Week 12	Day 85	Day 72 to 119
Week 26 (DBT EOT)	Day 183	Day 134 to 202

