Week 26 (DBE Baseline)	Day 183	Day 134 to 202
Week 39	Day 274	Day 250 to 320
Week 52 (DBE EOT)	Day 365	Day 321 to 396
Follow-up until Week 32 (DBT EOS)	6 weeks after EOT for DBT	NA
Follow-up until Week 58 (DBE EOS)	6 weeks after EOT for DBE	NA

(3) Safety data

Table 4 Analysis Visit Window for safety data

Analysis Visit	Nominal day	Analysis Visit Window
Screening*	Day -42*	-
Baseline*	First dose day*	NA*
Week 2	Day 15	Day 2 to 22
Week 4	Day 29	Day 23 to 42
Week 8	Day 57	Day 43 to 71
Week 12	Day 85	Day 72 to 119
Week 16 (Only for Norway site)	Day 113	-
Week 18(Only for Japan and Canada site)	Day 127	-
Week 20 (Only for Norway site)	Day 141	-
Week 26 (DBT EOT)	Day 183	Day 134 to 190

Week 26 (DBE Baseline)	Day 183	Day 134 to 190
Week 28	Day 197	Day 191 to 211
Week 30 (Only for Germany site)	Day 211	-
Week 32	Day 225	Day 212 to 249
Week 36 (Only for Norway, Germany and Canada site)	Day 253	-
Week 39	Day 274	Day 250 to 320
Week 43 (Only for Norway site)	Day 302	-
Week 47 (Only for Norway site)	Day 330	-
Week 52 (DBE EOT)	Day 365	Day 321 to 396
EOT for DBT (LOCF)	Day 182 or discontinued during DBT	The latest visit during DBT period
EOT for DBE (LOCF)	Day 365 or discontinued during DBE	The latest visit during DBE period
Follow-up until Week 32 (DBT EOS)	6 weeks after EOT for DBT	NA
Follow-up until Week 58 (DBE EOS)	6 weeks after EOT for DBE	NA

* For liver function markers (ALT, AST, GGT, ALP, direct and total bilirubin), the mean value of two numerical values at screening visit and at randomization visit (the first dose day) will be treated as a baseline value.

The date of the first dose of study drug is defined as Day 1.

Unless otherwise specified, baseline will be the last observed value of the parameter of interest prior to the first intake of study drug (for DBT) or will be the available value of parameter of Week 26 (for DBE).

For other visits, if there are multiple data in a window, the closest data to nominal day will be used. If the distance to the nominal day is the same, the data of later date will be used.

According to country specific protocol for Japan, Norway, Germany and Canada, liver function markers (ALT, AST, GGT, ALP, direct and total bilirubin) will be measured at each country specific visit in each country.

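### Extension change scores and the 66-minute responder rule start from Week 26, an on-treatment value for continuing MT-7117 groups, so a maintained effect counts as zero change and non-response

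*SAP*

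**What the plan says.** **Baseline rule.** SAP 7.3 gives a default that applies unless something else is specified. For the double-blind treatment period (DBT), baseline is the last value before first intake. For the double-blind extension (DBE), it "or will be the available value of parameter of Week 26 (for DBE". Table 2 has a row labelled "Week 26 (DBE Baseline" covering diary Days 169 to 182, the same days as the DBT end-of-treatment window. Table 3 does the same for non-diary efficacy data. In the section 9.3 diary table, the DBE change-from-baseline column starts at that row and has no mark on the original Baseline row.

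**Endpoints.** SAP 2.3.4 lists "Change from baseline in average daily sunlight exposure time (minutes) to first prodromal symptom" at each time point. It also lists a responder percentage "defined by within-subject meaningful change of 66 minutes increase from baseline at each time point". Neither names a different baseline, so the default governs.

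**Groups.** SAP 3.1 states: "Subjects that received MT-7117 during the blinded period will continue the DBE in the same treatment arm and remain blinded". SAP 7.1 reports four DBE groups: two that continue a dose and two switched from placebo.

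**Protocol.** Protocol 14.3 defines baseline for the sunlight-exposure endpoint as the mean over a 14-day window before Day 1. It then lists Weeks 52 and 58 among the post-baseline points. SAP section 1 says that the SAP supersedes the protocol on analysis details. SAP section 10 reports no changes to the analysis.

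**The concern.** The extension is where the plan can show whether a benefit lasts beyond 26 weeks. For a continuing subject, the Week 26 value already contains whatever the drug has done. The 66-minute rule then asks for a further 66 minutes on top of that gain, which is not what a threshold for meaningful within-subject change is meant to test. For a subject switched from placebo, the same rule measures gain from a value before active drug. One row of a table therefore carries two different quantities under one label.

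Melanin density has a related gap. Protocol 7.2 says of the 6-week follow-up, "which is considered a sufficient duration to evaluate pigmentation recovery and safety of subjects". Recovery means return to the pre-treatment level. In continuing subjects, change from Week 26 shows a full return as a decrease of unknown completeness, not as zero.

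The protocol and the SAP also define the Week 52 and Week 58 diary change differently, and section 10 does not say so.

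**Working it through.** **1. Plan's own figures.** The documents give no power or sample size for the extension. The effect sizes and SD used below come from SAP 3.3 (protocol 14.2): differences of 57 and 52 minutes, SD 79.3, 42 completers per arm, two-sided 0.05.

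- Standard error: 79.3 × √(2/42) = 17.3.
- 57 minutes: 57/17.3 = 3.29, and Φ(3.29 − 1.96) = 0.91, as stated.
- 52 minutes: 52/17.3 = 3.00, and Φ(3.00 − 1.96) = 0.85 taken alone. A simulation of the fixed sequence (400,000 runs, shared placebo arm) gives 0.79 for passing both, as stated.
- 42/0.8 = 52.5, so 53 per arm and 159 in total, as stated.

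**2. One subject, effect fully maintained.** The values are chosen for illustration: 30 minutes before Day 1, 130 at Week 26, 130 at Week 52.

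| Baseline | Change at Week 52 | 66-minute responder |
|---|---|---|
| Days −14 to −1 | 130 − 30 = 100 | yes |
| Week 26 | 130 − 130 = 0 | no |

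To count as a responder from Week 26, this subject would need 130 + 66 = 196 minutes, which is 166 above the pre-treatment value. The zero does not depend on the size of the maintained gain.

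**3. Group illustration.** Assumptions, none given in the documents for the extension:

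- changes are normal;
- change from pre-treatment has SD 79.3 at both Week 26 and Week 52;
- the mean gain of 52 or 57 minutes is fully maintained and the placebo change is zero;
- the Week 26 and Week 52 changes have correlation ρ between 0.5 and 0.8.

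From the pre-treatment baseline, P(response) = 1 − Φ((66 − m)/79.3):

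- m = 52: 1 − Φ(0.177) = 43.0%
- m = 57: 1 − Φ(0.113) = 45.5%

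From Week 26, the mean change in a continuing group is 0 and its SD is 79.3 × √(2(1 − ρ)). For a switched group gaining 52 to 57 minutes after Week 26, the same SD is used with that mean.

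| ρ | SD of change | Continuing, mean 0 | Switched, mean 52 to 57 |
|---|---|---|---|
| 0.5 | 79.3 | 20.3% | 43.0% to 45.5% |
| 0.7 | 61.4 | 14.1% | 41.0% to 44.2% |
| 0.8 | 50.2 | 9.4% | 39.0% to 42.9% |

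The continuing-group rate is the same for any maintained mean gain. All of it is within-subject variation between the two windows. Under these assumptions the continuing and switched groups benefit equally, yet the table shows 9% to 20% beside 39% to 45.5%.

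**4. Sensitivity to the placebo change.** The documents do not give it. If it were 50 minutes, the maintained gains would be 102 and 107 minutes. The pre-treatment-baseline rates would be 67.5% and 69.7%, and the Week 26 rates for continuing groups would not move.

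**The case against.** Much of the case on the other side stands.

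- **Nothing confirmatory is touched.** The DBE endpoints are exploratory and, under SAP 8.2.3, summarised without models. H1 to H12 concern Week 26 or the 26-week period.
- **A near-zero change can be read correctly.** The column is labelled as change from Week 26, and continuing and switched groups are shown separately. A careful reader would take zero as maintenance. A reader might infer that the tables would show loss of effect, but loss would appear as a negative change. The responder percentage is the real trap, because it cannot be reconstructed from mean values.
- **Absolute values are also reported.** SAP 8.2.3 summarises melanin density itself and SAP 8.3.2 summarises absolute laboratory values, so a return towards pre-treatment means could be seen. Subjects who do not enter the DBE have Week 32 melanin in the DBT analysis, from the pre-treatment baseline. What is missing is the within-subject change.
- **Liver markers may be exempt.** Footnotes to Table 4 and section 9.3 define their baseline as the mean of the screening and randomization values. Whether this also governs the DBE is not stated.
- **The protocol leaves room.** Protocol section 14 assigns extension methods to the final SAP, and the SAP claims precedence. This makes Week 26 the operative rule, but it does not make the section 10 statement accurate.

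Three further inferences are not supported. The Week 52 PGIC responder involves no baseline subtraction, so the rule does not affect it. The plan does not throw away a season-matched comparison merely because Week 52 and the pre-treatment window fall at the same time of year: the data are kept and listed, and protocol 7.3 reports no seasonal impact on the Phase 2 primary endpoint. A contrast as wide as 67% against 14% needs an assumed 100-minute gain (and ρ = 0.7). Beside a 57-minute treatment difference, that implies a placebo change of 43 minutes, which the documents do not give.

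**Conclusion.** The point holds for the extension diary change scores and, above all, for the 66-minute responder rule. That a subject with an unchanged value scores 0 and is a non-responder is arithmetic and needs no assumption. At group level, the understatement with the plan's own effect sizes is roughly 23 to 36 percentage points (43.0 − 20.3 to 45.5 − 9.4), given normality, SD 79.3, zero placebo change, full maintenance and correlation 0.5 to 0.8. A positive placebo change would widen it.

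The same default leaves within-subject pigmentation recovery at Week 58 unmeasured in continuing subjects, although absolute means soften this. The difference from protocol 14.3 is undeclared and needs reconciling whichever baseline is preferred. The consequence is confined to the interpretation of exploratory, descriptive long-term summaries.

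**What to change.** 1. In SAP 7.3 and 2.3.4, compute the extension diary change scores and the 66-minute responder rule from the pre-treatment baseline (Days −14 to −1, with the fallback window already in the Table 2 footnote) for all four groups.
2. Add change from the pre-treatment value for the other extension change scores, including melanin density through Week 58 and the non-liver laboratory parameters.
3. Keep change from Week 26 as a separately labelled column. It shows maintenance in continuing groups and onset in groups switched from placebo.
4. State which baseline applies to liver markers in the DBE.
5. Reconcile with protocol 14.3, mark the Baseline row in the section 9.3 DBE columns, and record any remaining departure in SAP section 10.

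Cost: SAP wording, one extra baseline flag and additional descriptive columns. No new data are needed. The downside is more extension tables.

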Fitzpatrick skin type assessment ^s	X		X		X		X	X		X	X
Pregnancy test ^t	X	X	X		X		X	X		X	X
PK sampling (blood) ^y		X		X		X	X		X	X	
Blood sampling for PGx ^b		X									
Dispensing of study medication	X	X	X		X		X	X		X	
Medication accountability		X		X		X		X		X	
Subject Question for study medication ^k						X					
PROMIS-57		X				X	X		X	X	X
PGIC				X			X			X	
PGIS		X	X		X		X		X	X	X
EOT/Exit interview questionnaire ^l						X					
Sunlight exposure diaries ^m											
In-clinic sunlight exposure test ⁿ	X									X	

Study Period	Screening		Double-blind Treatment					Double-blind Extension			Follow-up	
	Visit Number	Visit 1	Visit 2 (Randomization)	Visit 3 ^g	Visit 4	Visit 5 ^g	Visit 6	Visit 7 ^h (EOT/ Rand)	Visit 8 ^g	Visit 9 ^g	Visit 10	
Study Week	Week -6 to Week 0		Week 2	Week 4	Week 8	Week 12	Week 26	Week 28	Week 32	Week 39	Week 52	Week 32 or 58
Study Day ± Window	Day -42 to Study Day ^a	Day 1	Day 15±5	Day 29±7	Day 57±7	Day 85±7	Day 183±7	Day 197±7	Day 225±7	Day 274±7	Day 365±7	Day 407±7
Melanin density evaluation		X		X		X	X				X	X
Nevi evaluation ^o		X		X		X	X				X	X
Concomitant medication												
Adverse events												

Abbreviations: DBE = double-blinded extension; ECG = electrocardiogram; EOS = end of study; EOT = end of treatment; PGIS = Patient Global Impression of Change; PGIS = Patient Global Impression of Severity; PGx = pharmacogenomic(s); PK = pharmacokinetic; PROMIS = Patient-Reported Outcomes Measurement Information System.

^a A minimum of 7 days of outside exposure data is required in the 14 days prior to randomization.

^b Blood samples will be collected for PGx analysis for those subjects who have specifically given informed consent/assent for optional PGx analysis at Visit 2.

^c Complete physical examination will be performed at Visit 1 and an abbreviated physical examination will be performed at all other specified time points.

^d Vital signs include measurement of sitting blood pressure, respiratory rate, pulse rate, and body temperature.

^e ECG will be assessed at Visit 7 for subjects who do not elect DBE. For subjects that received MT-7117 during the blinded period will continue the DBE in the same treatment arm and remain blinded. Subjects that received placebo will be randomized to receive MT-7117 [REDACTED] or [REDACTED] in 1:1 ratio for the 26 weeks DBE period. For subjects with the [REDACTED] dose will be administered without re-randomization.

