^b Blood samples will be collected for PGx analysis for those subjects who have specifically given informed consent/assent for optional PGx analysis at Visit 2.

Statistical Analysis Plan
Protocol No. MT-7117-G01

- c Complete physical examination will be performed at Visit 1 and an abbreviated physical examination will be performed at all other specified time points.
- d Vital signs include measurement of sitting blood pressure, respiratory rate, pulse rate, and body temperature.
- e ECG will be assessed at Visit 7 for subjects who do not elect DBE. For subjects who elect DBE, ECG will be assessed at Visit 11.
- f All study subjects who elect to participate in the 26-weeks DBE will be re-randomized. Subjects that received MT-7117 during the blinded period will continue the DBE in the same treatment arm and remain blinded. Subjects that received placebo will be randomized to receive MT-7117 [REDACTED] or [REDACTED] in 1:1 ratio for the 26 weeks DBE period. For subjects with [REDACTED], the [REDACTED] dose will be administered without re-randomization.
- g At Visits 3, 5, 8, and 9, subjects may have mobile units or in-clinic visits to measure liver function markers (ALT, AST, GGT, ALP, direct and total bilirubin). Blood samples for liver function markers will be shipped to the central laboratory.
- h Plasma total porphyrins and erythrocyte protoporphyrin will be assessed at Visits 1, 4, 6, 7, 10, and 11.
- i For female subjects of child-bearing potential, a serum pregnancy test will be performed at Visit 1 and a urine pregnancy test will be performed at Visits 2, 4, 6, 7, 10, 11, and 12.
- j For subjects who are ≥ 18 to ≤ 75 : PK blood samples for MT-7117 will be collected and processed at Visit 2 (pre-dose), Visits 4, 6, 10, and 11 (any time), and Visit 7 (at the visit and 3 to 4 hours after the first PK sample collection [both post-dose]). Date and time of most recent dose, and date and time of PK sample collection will be recorded. Subjects who are ≥ 12 to ≤ 17 years old will have 9 PK samples at 3 time points collected. Visit 2 at 2, 4, 6, and 8 hours post-dose, Visit 6 at pre-dose and 3 hours post-dose, and Visit 7 at pre-dose and 2, and 4 hours post-dose.
- k Subjects will be asked whether they believe they received active or placebo treatment.
- l EOT/Exit interview will only be performed in selected countries.

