7.2.3.3 Laboratory Tests

(1) Criteria for pre-defined limit

Liver function:

- ALT $\geq 10 \times \text{ULN}$
- $8 \times \text{ULN} \leq \text{ALT} < 10 \times \text{ULN}$
- $5 \times \text{ULN} \leq \text{ALT} < 8 \times \text{ULN}$
- $3 \times \text{ULN} \leq \text{ALT} < 5 \times \text{ULN}$
- $1 \times \text{ULN} \leq \text{ALT} < 3 \times \text{ULN}$

The above same criteria will be applied to AST.

- Total Bilirubin $\geq 2 \times \text{ULN}$
- $1 \times \text{ULN} \leq \text{Total Bilirubin} < 2 \times \text{ULN}$

7.2.3.4 12-Lead ECG

(1) Criteria for pre-defined limit

12-lead ECG:

- Baseline QTc $< 450 \text{ msec}$ and $> 500 \text{ msec}$ at any post baseline
- Baseline QTc $< 450 \text{ msec}$ and $500 \text{ msec} \geq \text{QTc} > 480 \text{ msec}$ at any post baseline
- Baseline QTc $< 450 \text{ msec}$ and $480 \text{ msec} \geq \text{QTc} > 450 \text{ msec}$ at any post baseline
- Increase from baseline in QTc $> 30 \text{ msec}$, 60msec at any post baseline

The above same criteria will be applied to QTcF and QTcB.

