8.3 Safety Assessments

Safety assessments of DBT period data and DBE period will be made on the SAF1 and SAF2 populations, resepectively. All data will be listed.

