8.3.3 Vital Signs

Absolute values and change from baseline will be summarized descriptively and shift table of clinically relevant categories (Normal, Abnormal(Not Clinically Significant, Clinically Significant)) from baseline to EOT will be also presented for the following parameters .

- Systolic Blood Pressure (mmHg)
- Diastolic Blood Pressure (mmHg)
- Pulse Rate
- Respiratory Rate
- Body Temperature (°C)
- Body Weight (kg)

8.3.4 12-Lead ECGs

Absolute values and changes from baseline will be descriptively summarized and shift table of clinically relevant categories (Normal, Abnormal(Not Clinically Significant, Clinically Significant)) from baseline to EOT will be also presented for the following parameters.

- Heart Rate (bpm)
- PR (msec)
- RR (msec)
- QRS (msec)
- QT (msec)
- QTcF (msec)
- QTcB (msec)

A summary table of the number and percentage will be provided for subjects who met the 12-lead ECG criteria of QTcF and QTcB for pre-defined limit as numerator.

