9.3 Analysis Visits to Report

eDiary:

Analysis Visit	Apply to					
	Analysis for DBT period data			Analysis for DBE period data		
	Change from baseline	Total time / number of days / severity of phototoxic reaction during 26 weeks	Maximum severity of phototoxic reaction	Change from baseline	Total time / number of days / severity of phototoxic reaction during 26 weeks	Maximum severity of phototoxic reaction

Baseline	X		X			
Week 2	X					
Week 4	X					
Week 6	X					
Week 8	X					
Week 10	X					
Week 12	X					
Week 14	X					
Week 16	X					
Week 18	X					
Week 20	X					
Week 22	X					
Week 24	X					
Week 26 (DBT EOT)	X					
During 26 weeks(DBT)		X	X			X
EOT for DBT			X			
Follow-up until Week 32(DBT EOS)	X					
Week 26 (DBE Baseline)				X		
Week 28				X		
Week 32				X		
Week 39				X		
Week 52 (DBE EOT)				X		X
During 26 weeks(DBE)					X	
EOT for DBE						
Follow-up until Week 58 (DBE EOS)				X		

Efficacy except for eDiary:

Analysis Visit	Apply to
	Analysis for DBT period data Analysis for DBE period data

Statistical Analysis Plan
Protocol No. MT-7117-G01

Mitsubishi Tanabe Pharma Development America

	PROMIS-57	PGIC	PGIS	In-clinic symptom exposure test	Melanin density evaluation	PROMIS-57	PGIC	PGIS	In-clinic symptom exposure test	Melanin density evaluation
Baseline	X			X	X					
Week 4		X	X		X					
Week 12	X		X		X					
Week 26 (DBT EOT)	X	X	X	X	X					
Follow-up until Week 32(DBT EOS)	X		X		X					
Week 26 (DBE baseline)						X	X	X	X	X
Week 39						X		X		
Week 52 (DBE EOT)						X	X	X	X	X
Follow-up until Week 58(DBE EOS)						X		X		X

Safety:

Analysis Visit	Apply to							
	Analysis for DBT data				Analysis for DBE data			
	Laboratory Tests	Vital Signs	12- Lead ECGs	New evaluation	Laboratory Tests	Vital Signs	12- Lead ECGs	New evaluation
Screening	X***	X		X				
Baseline	X***	X	X					
Week 2	X (liver function)							
Week 4	X	X		X				
Week 8	X (liver function)							
Week 12	X	X		X				
Week 16	X**							

Week 18	X**							
Week 20	X**							
Week 26 (DBT EOT)	X	X	X	X				
EOT for DBT (LOCF)	X	X	X	X				
Follow-up until Week 32 (DBT EOS)	X	X		X				
Week 26 (DBE Baseline)					X	X	X	X
Week 28					X*			
Week 30					X**			
Week 32					X*			
Week 36					X**			
Week 39					X	X		X
Week 43					X**			
Week 47					X**			
Week 52 (DBE EOT)					X	X	X	X
EOT for DBE (LOCF)					X	X	X	X
Follow-up until Week 58(DBE EOS)					X	X		X

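### The extension-period ECG baseline is set at Week 26, where the global schedule plans no ECG for anyone who enters the extension

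*SAP*

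**What the plan says.** - **Baseline rule (SAP 7.3).** Unless another rule is given, the double-blind treatment (DBT) baseline is the last value before first intake of study drug. The DBE baseline "will be the available value of parameter of Week 26 (for DBE"). Table 4 gives that visit the window Day 134 to 190. The section has a special baseline rule for liver markers and none for ECG.
- **Reporting visits (SAP 9.3, safety table).** In the DBE columns, 12-lead ECG is marked at "Week 26 (DBE Baseline") and at Week 52. The DBE columns carry no mark in the pre-treatment baseline row.
- **Schedule (SAP Table 1, footnote e).** ECG is assessed at "Visit 7 for subjects who do not elect DBE. For subjects who elect DBE, ECG will be assessed at Visit 11". Protocol Table 9-1, footnote e, has the same Visit 7 condition: "ECG will be assessed at Visit 7 for subjects who do not elect DBE". Visit 7 is Week 26 and Visit 11 is Week 52.
- **Outputs (SAP 8.3 and 8.3.4).** "Safety assessments of DBT period data and DBE period will be made on the SAF1 and SAF2 populations" respectively, so the ECG outputs apply to the extension too. For ECG: "Absolute values and changes from baseline will be descriptively summarized and shift table of clinically relevant categories", from baseline to end of treatment, plus a table of subjects meeting the "ECG criteria of QTcF and QTcB for pre-defined limit as numerator".
- **QTc criteria (SAP 7.2.3.4).** Three categories require a baseline QTc below 450 msec, and two are increases from baseline (above 30 and above 60 msec). "The above same criteria will be applied to QTcF and QTcB".

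**The concern.** The analysis rule and the assessment schedule point to different visits. The rule looks for the extension baseline ECG at Week 26. The schedule obtains a Week 26 ECG only from subjects who will not be in the extension analysis. A programmer who follows the SAP literally finds no planned baseline for any extension subject.

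ECG at baseline and end of treatment is a named safety endpoint (SAP 2.3.5) under a long-term safety objective. The extension would report where ECG values stood at Week 52, but not how far they had moved or who crossed a QTc threshold.

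The change tables would show the gap openly as n=0. The QTc criteria table might not. SAP 8.3.4 defines only its numerator, the default denominator in SAP 6.1 is everyone in the group, and SAP 9.1 leaves a zero percentage blank. A group in which nobody could be evaluated could then look like a group with no outliers.

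**Working it through.** No figure in the plan needs reproducing. This is a consistency check, so the passages are set side by side.

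**Step 1: who has a planned Week 26 ECG under the global schedule?**

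| Subject | Planned end-of-treatment ECG (footnote e) | In the DBE analysis? |
|---|---|---|
| Completes DBT, declines DBE | Visit 7 (Week 26) | No |
| Terminates early in DBT | Early-termination Visit 7 (footnote p) | No; footnote p bars dispensing of extension drug |
| Enters DBE | Visit 11 (Week 52) | Yes |

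Planned Week 26 ECGs among DBE entrants = 0. This holds at any uptake rate.

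**Step 2: which extension outputs need that baseline?**

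- Change from baseline: heart rate, PR, RR, QRS, QT, QTcF and QTcB = 7 parameters.
- Shift from baseline to end of treatment: Protocol 10.9.3 collects one overall rating per ECG (normal, or abnormal with or without clinical significance). The data therefore support one shift of that rating.
- QTc criteria: 3 categories conditional on baseline + 2 increases = 5. Two corrections give 5 x 2 = 10 rows. The four DBE treatment groups in SAP 7.1 give 10 x 4 = 40 cells.

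All of these need a baseline. Absolute Week 52 values do not, and they can still be summarised.

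**Step 3: can anything else supply the baseline?**

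- The rule refers to an available value, so an unscheduled ECG on Days 134 to 190 would qualify. It would not be planned data.
- SAP 3.2 refers to separate schedules for Japan, Norway, Germany and Canada. Those protocols are not among the documents.
- The ECG taken before first dose would serve, and SAP 7.3 already uses it for DBT. The DBE rule does not point to it.

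**Step 4: does the same footnote affect DBT?** To a lesser degree. Planned post-baseline ECGs in DBT come only from subjects who decline DBE or terminate early. The DBT baseline itself is sound, so this is a question of denominator and labelling.

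**The case against.** The strongest objection is Protocol 14.3.3, which defines an ECG baseline as the last valid Day 1 assessment before double-blind dosing. SAP 7.3 yields where another rule is specified, and SAP 10 declares no changes from the protocol, so a programmer could treat Day 1 as the fallback. This does not close the gap. SAP 1 says that the SAP supersedes the protocol on statistical analysis, Protocol 14 leaves extension methods to the final analysis SAP, and SAP 9.3 places the DBE ECG baseline at Week 26. For the same reasons, a reader should not infer that the two documents directly contradict each other on the extension baseline: the protocol did not set one.

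Some of the evidence is out of sight. The ECG rows of both schedule tables are broken in the available text, so the check rests on footnote e, which is complete in the SAP. In the protocol text, the rest of the footnote runs into the next one. SAP 7 says that analysis visits were confirmed at data review meetings whose minutes are not included, and four country schedules are missing. This stands as a limit: the zero is a statement about the global schedule, not about the ECGs actually recorded.

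The consequence is also modest. The tables are descriptive, all data are listed (SAP 8.3), and clinically significant ECG abnormalities are reported as adverse events (Protocol 10.9.3). That is correct, and it rules out the inference that an ECG safety signal would go unseen.

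On the denominator, SAP 6.1 already permits percentages out of subjects with available data. The SAP therefore needs to invoke that option, not create one.

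**Conclusion.** The inconsistency is real and should be corrected before the final analysis. Under the global schedule, 0 DBE entrants have a planned Week 26 ECG. The seven change-from-baseline summaries, the shift of the overall rating and the ten QTc rows in the extension have no planned baseline. No efficacy endpoint, estimand, alpha or power is involved. The finding assumes that footnote e governs any Visit 7 ECG mark in the schedule, and that no separate ECG rule sits in documents not provided.

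Three stronger readings are tempting and not supported:

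- **Seven empty shift tables.** SAP 8.3.4 lists seven parameters under the shift wording, but Protocol 10.9.3 collects one overall rating per ECG.
- **A quantified dilution of the DBT QTc percentages.** Any such figure needs the DBE uptake rate, which the documents do not give. If uptake is equal across arms, ratios between arms do not change.
- **Loss of extension ECG information.** Week 52 values remain, and change can be computed from the ECG before first dose.

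**What to change.** 1. In SAP 7.3, define the DBE ECG baseline as the last ECG before the first study dose. This is already the DBT rule and is in line with Protocol 14.3.3.
2. In SAP 9.3, show that baseline in the DBE columns and reconcile the Week 26 DBE-baseline ECG entry with footnote e. Any Week 26 ECG that exists can stay as a visit value.
3. In SAP 8.3.4, invoke the available-data option of SAP 6.1 for the QTc criteria. The denominator is subjects with a baseline and at least one post-baseline ECG in the period. Print that n, so that not evaluable is not shown as no outliers.
4. Footnote the DBE tables that change spans both periods: 52 weeks of drug for continuing subjects, and 26 weeks of placebo plus 26 weeks of drug for placebo switchers. Footnote the DBT tables that planned post-baseline ECGs come only from subjects who decline DBE or terminate early.

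SAP 10 needs at most a note. The cost is SAP wording and table shells; no added ECG is needed. Two trade-offs follow: the extension change no longer isolates the extension period, and the DBT QTc percentages rest on a smaller n. Reporting extension ECGs as absolute values only, with a footnote, would also remove the inconsistency, but it would give up the change, shift and QTc results that collected data can support.
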